5.8. Measures

Assessment of participant characteristics and/or performance will involve a multidimensional set of instruments administered by trained research interviewers. See **Figure 2**, for a schematic of measures and when they are administered. Sources of information will include: (1) self-report; (2) official records; (3) urine drug screening results; and (4) treatment program records. Assessment at baseline will provide information on participant characteristics and pre-incarceration histories of substance use, substance use treatment, crime, incarceration, and HIV risk behavior. Participants in both conditions will be paid \$50 cash for each follow-up visit. Participants

will not be paid for baseline assessments in prison due to the fact that such payments may be viewed as coercion.

5.8.1. XR-NTX Adherence. Data on post-release treatment status will be obtained from GLCC records. Treatment status will be measured at each follow-up point by whether or not a participant received an injection of XR-NTX at each follow-up point (yes v. no). We will also collect data on whether a person entered outpatient treatment (yes v. no) and the type of services utilized. Treatment duration for individuals who end treatment will be calculated based on the last date of clinic attendance (if a participant fails to receive his/her injection by day 37 s/he would be considered a drop-out). Thirty seven days is used in our current XR-NTX studies as this is how long the medication typically protects the participant. We will also collect data on whether or not participants entered other types of treatment. Follow-up assessments will collect self-report data on reasons why participants entered, did not enter, or dropped out of treatment.

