5.8.2. Addiction Severity Index (ASI) with Timeline Follow-Back (TLFB). The ASI is a standardized 40-60 minute measure widely used in research to quantify problem areas in substance-using populations.^{89,90} This instrument has excellent inter-rater and test-retest reliability.^{89,90} We will also collect data on substance use frequency and criminal activity to cover the entirety of the follow-up periods post-baseline. In addition, we will use the DSM-5 opioid-related-disorder classification⁹¹ to assess opioid use severity (mild, moderate, severe). In addition to the ASI, we will collect baseline data on crime severity which is determined on the basis of a 7-point scale (a higher number indicating greater severity of criminal involvement) and classifies crime severity according to the most serious level of criminal activity in their lifetime prior to the index incarceration.⁹²

5.8.3. Biological Assays. Urine will be tested on-site with CLIA waived QuikScreen cups using an immunochromatographic assay for rapid (2-5 minute) qualitative results based on SAMHSA-standard cutoffs for alcohol (20mg/dl or 0.02% BAC), amphetamine/methamphetamine (1,000 ng/ml), cannabis (50 ng/ml), cocaine/ benzoylecgonine (150 ng/ml), and opiates/morphine (2000 ng/ml). In addition, we will test for methadone and buprenorphine, and for commonly abused prescription drugs (*oxycodone, hydrocodone, and codeine*) (100 ng/ml), and for *Fentanyl* (10ng/ml). Results will be used as outcome measures of heroin and other opioid use as well as to check on the validity of self-reported drug use information. Urine samples will not be obtained on the approximately 10% of participants who we expect to be re-incarcerated. Those participants in methadone or buprenorphine treatment who screen positive only on their respective treatment medication will be counted as negative for their urine drug screening results.

5.8.4. Risk Assessment of Battery (RAB). This self-administered questionnaire, designed to identify individuals engaging in acts that could transmit HIV and other infectious diseases,⁹³ contains 45-items consisting of three scales: a drug risk, sexual behavior risk, and an overall scale.

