6.4. Explanatory Variables. The predictor variables in all statistical models can be categorized as either Treatment Variables, Covariates, or Control Variables. (From a statistical viewpoint, this categorization is arbitrary and is utilized here simply for ease of presentation.)

Treatment Variables. There will be a single treatment variable: Treatment Condition (XR-NTX-MMTx v. XR-NTX+OTx).

6.4.1. Covariates. Three additional predictor variables – Age, Gender, and age of onset of criminal activity – will be included as “main effects” in all analyses. These “main effects” test for the unique contribution of each of these variables in predicting outcome, above and beyond the effects of Treatment Condition. Each of these variables, as well as its respective interaction with Treatment Condition, will be included as a predictor in order to examine for potential differences in treatment outcome as a function of each covariate, and whether any of these three covariates moderate treatment efficacy.

6.4.2. Control Variables. Finally, because participants may know one another through contact at their respective prison, it is possible that participants' responses within a given prison will not be entirely independent of each other. This potential lack of independence must be controlled for by including Prison nested within Treatment Condition and Participants nested within Prison nested with Treatment Condition as random factors. [Although neither of these two effects represents a substantive effect of interest, both must be included in order to produce unbiased estimates and tests of significance for Treatment Condition.]

6.4.3. Time. Finally, the “repeated factor” in the statistical analysis of all outcome variables measured repeatedly will be assessment Time point, which will allow for the evaluation of both *differential course and impact* of the interventions as a function of the “between-subjects” Treatment Condition factor. (For information regarding which outcome variables are measured at what assessment time points, see **Figure 2**, above.)

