6.7. Power. Stroup¹⁰¹ (also see Littell et al.¹⁰²) has outlined a four-step procedure to estimate power for general linear mixed models, which can also be applied to generalized linear mixed models as occur in the proposed study. This procedure was implemented in the current case. For each of the number of Times outcomes were measured (4, 5, 6, 7, or 9), three datasets for each hypothesis were created, assuming the dependent variable was continuous and normally distributed, discrete and Poisson distributed, or dichotomous and binomially distributed. For the normally distributed case, the only non-null effect in the model was the hypothesized effect of interest, with the XR-NTX-OTx condition mean set at 1 at Time 1, decreasing by .1 at each subsequent Time point, while the XR-NTX+MMTx condition means were set at 1 at Time 1, and then adjusted to reflect “small”¹⁰³ mean differences (.2 of the standard deviation at subsequent Time points) consistent with the hypothesis of interest. [Time was not included in the estimation of power for the criminal justice outcomes because these outcomes are measured only at 12-month post-baseline assessment.] Similar specifications were made for the datasets with outcomes following the Poisson and binomial distributions. Finally, observations were dropped from the data consistent with the expected loss of approximately 10% of participants at the 12-month assessment (see **Participant Attrition**, above). Hence, power was estimated for a design in which the effects were unbalanced in a manner similar to what was expected to occur in the proposed research. Therefore, simulations were conducted under what might be considered “worst-case scenarios.” Power was then estimated for three different covariance structures (compound symmetric heterogeneous, first-order autoregressive heterogeneous, and unstructured) of the observations over Time. [Covariance structures can be specified for GLiMM models independent of the location (e.g., mean) structure, so it was only necessary to create a single dataset for the three cases.] Assuming a sample size of 240 and $\alpha=.05$, the resulting power values ($1 - \beta$) for the Treatment Condition X Time effect varying between .81 and .85 in the simulations. From a more rudimentary and slightly less accurate perspective, assuming the primary outcome measures follow a normal distribution rather than binomial or Poisson distributions, power calculations based on the set correlation method¹⁰⁴ can be used to calculate effect sizes for desired power, including under the extremely conservative assumption that no other effect in the model is significant (with the resulting effect size estimates likely to be slight underestimates). In this case, assuming $\alpha=.05$ and $N=216$ due to attrition (see **Participant Attrition**, above) in order to remain conservative, an effect size of $f^2=.037$ in the population associated with a Treatment Condition main effect for statistical models in which there is no Time effect (e.g., reincarceration) and effect sizes ranging from a minimum $f^2=.046$ to a maximum $f^2=.072$ for the Treatment Condition X Time effects associated with the 4, 5, 6, 7, or 9 Time points for statistical models in which there is a Time effect, would yield a power of .8 for the respective effect. These effect sizes fall toward the “small-to-medium” range, with $f^2=.02$ considered a “small” effect and $f^2 = .15$ a “medium” effect.¹⁰³ In other words, and imprecisely, under the assumption that the effect in the population was $\geq .037$ or $\geq .072$, for the Treatment Condition and Treatment Condition X Time effects, respectively, there is an 80% chance of concluding that effect is significant if α is set to .05 and 216 participants are assessed at 12-month follow-up. *Power calculations do not utilize any estimates of treatment efficacy from prior studies. This latter approach to power analysis, although once popular, is often quite limited, as is the case for the proposed study, in that prior studies may have examined populations that are not comparable to the population in the proposed study and/or do not include the same experimental or control conditions, and in all cases, the effect sizes reported in prior studies are generally subject to wide fluctuation due to sampling variability.*¹⁰⁵ Power was calculated to detect a stated effect size, as detailed in the proposal, an approach consonant with more recent writings regarding power analysis.

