
6.8. Supplementary Analyses. We will tabulate (and test for treatment condition differences) for the relative frequency of each adverse event (AE) in each condition, where the examination is based on the proportion of

individuals who experience the AE, and the number of that AE reported. In addition, we will tabulate and test for treatment condition differences) for the relative frequency of opioid overdoses in each condition, where the examination is based on the proportion of individuals who report overdoses during the 12-months post-release. We will also calculate mean scores of cravings at each follow-up.

6.9. Additional Process Data *We will collect three additional process variables: (1) data on housing stability at each follow-up visit that will utilize a checklist to describe the participant's place of residence and the level of stability; (2) data on the distance travelled from place of residence to Glenwood Life Counseling Center (GLC) for participants randomized to TAU; and (3) data on the number of counseling sessions received during the course of the study (this will account for any community counseling received during treatment).*

6.10. Follow-up Analyses. *Follow-up analyses will include select covariates in the model, with a focus on the covariate X BI Intervention Condition (X Time, if an outcome is measured repeatedly). These follow-up analyses can be viewed as either sensitivity analyses or as subgroup analyses^{106,107} intended to map the population(s) for which the intervention is maximally useful and/or examine the robustness of the findings under uncertainty in the model. Possible covariates include: (1) crime severity, (2) opioid severity, (3) housing stability, (4) distance travelled from place of residence to treatment clinic; and (5) number of counseling sessions received.*

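### The main models for re-arrest and re-incarceration leave out the baseline crime severity score and the crime and incarceration histories that the trial already collects

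*Combined protocol and SAP*

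**What the plan says.** Section 6.4.1 applies the same three covariates to every outcome: "Three additional predictor variables – Age, Gender, and age of onset of criminal activity – will be included as “main effects” in all analyses". Each also enters as an interaction with treatment condition.

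Figure 2 takes re-arrest and re-incarceration from official records at month 12 only, defined as time to event. Section 6.5 says that for an outcome measured once at the end the mixed model reduces to a generalized linear model. Neither outcome therefore has a baseline value in its model, unlike opioid use, days of crime or the HIV risk scores.

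The trial does collect closely related baseline measures. Section 5.8 says that the baseline assessment covers "pre-incarceration histories of substance use, substance use treatment, crime, incarceration, and HIV risk behavior". Section 5.8.2 adds: "In addition to the ASI, we will collect baseline data on crime severity which is determined on the basis of a 7-point scale". Figure 2 also lists days of crime at baseline. Section 5.3 places the baseline assessment before randomisation.

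Of these, only crime severity is named as a covariate anywhere, in 6.10: "Possible covariates include: (1) crime severity, (2) opioid severity, (3) housing stability". That section concerns follow-up models focused on covariate-by-condition interactions. Crime and incarceration histories are named as covariates in no model. The plan gives no reason.

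For models without a Time effect, section 6.7 gives a power of .8 at "an effect size of $f^2=.037$ in the population associated with a Treatment Condition main effect for statistical models in which there is no Time effect", "assuming $\alpha=.05$ and $N=216$ due to attrition".

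**The concern.** Both outcomes belong to Aim 1 and to the superiority hypothesis in 5.9.2. Each participant contributes one observation, and randomisation is stratified by gender only, so a chance imbalance in criminal history is not controlled by design. Offending before the index incarceration is a natural candidate predictor of re-arrest and re-incarceration. Age of onset says when offending began, not how often or how seriously the person offended, or how often he or she was incarcerated.

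If these histories are prognostic, leaving them out keeps explainable variation in the error term, and a real effect of mobile treatment is somewhat more likely to be missed. A list of possible covariates in 6.10 also leaves the choice open until results are known.

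**Working it through.** **Inputs from section 6.7.** f2 = .037, alpha = .05, stated power .8, and N = 216 (240 × .90, from the "expected loss of approximately 10% of participants at the 12-month assessment"). The plan assumes that no other effect in the model is significant, that is, zero contribution from covariates.

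**Input assumed.** R2, the share of outcome variance left after the three planned covariates that the added baseline measures explain. The documents give no value, so a range is shown.

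**Step 1: reproduce the plan's figure.** Noncentral F with df1 = 1, df2 = 216 − 2 = 214 and lambda = f2 × N = .037 × 216 = 7.99. Power = .8035, which matches .8. (Equivalent standardised difference: 2 × √.037 = .385.)

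**Step 2: add covariates.** Replace f2 by .037/(1 − R2). The equivalent unadjusted sample size is 216/(1 − R2).

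| Added R2 | Correlation √R2 | f2 | lambda | Power | Equivalent N |
|---|---|---|---|---|---|
| 0 | 0 | .0370 | 7.99 | .804 | 216 |
| .05 | .22 | .0389 | 8.41 | .823 | 227 |
| .10 | .32 | .0411 | 8.88 | .843 | 240 |
| .25 | .50 | .0493 | 10.66 | .901 | 288 |

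**Step 3: where power may already stand.** If the three planned covariates explain 5% of the variance (assumed), power is already .823, and a further 10% of the remainder takes it to .861. If they explain 10%, the figures are .843 and .878. If official records cover all 240 participants (assumed), f2 = .037 gives .843 with no covariate at all, and .879 with an added R2 of .10.

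**Step 4: check with a binary outcome.** Logistic simulation with 108 per arm, likelihood-ratio test and 2,000 replicates. Control rates are assumed, and the treated rate is set so that f2 = .037. The Monte Carlo standard error of each figure is about √(.8 × .2/2000) = .009.

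| Control / treated rate | R2 = 0: unadjusted, adjusted | R2 = .10 | R2 = .25 |
|---|---|---|---|
| 50% / 31.4% | .787, .793 | .800, .832 | .791, .894 |
| 30% / 14.3% | .792, .796 | .819, .845 | .786, .881 |
| 19% / 6.4% | .817, .818 | .819, .848 | .819, .890 |
| 10% / 1.3% | .886, .880 | .905, .903 | .876, .909 |

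The last row has only about 216 × .056 = 12 events and is unstable. A useless covariate (R2 = 0) costs almost nothing in any row.

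**Step 5: which event rates are plausible.** The documents give two weak pointers. Section 5.8.3 expects about 10% to be re-incarcerated, but says so about urine collection, so the figure may not be cumulative. In the pilot (2.7.3), 31% of non-completers and 0% of the 10 completers were re-arrested. That is about .31 × 17 = 5 of 27, or roughly 19%.

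At such rates a given R2 needs a strong predictor. In separate logistic runs at about 19% events, an odds ratio of 1.5 per SD gave no gain (.819 v. .817) and 2.2 per SD gave .804 to .848. At 10% events, 2.2 per SD gave a correlation of only .21 and power of .807 to .824; a correlation of .30 needs an odds ratio of about 3.3 per SD.

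**Step 6: time to event.** A Cox simulation at N = 216 with about 53% events gave unadjusted and adjusted power of .85 and .86 at a covariate-event correlation of .20, .85 and .91 at .31, and .88 and .94 at .40. The gain is not an artefact of the normal approximation, but this event rate is favourable to it.

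**The case against.** The strongest case is that covariate choice in a randomised trial is a matter of efficiency, that omission does not bias the comparison, and that the plan is not as bare as it may look. Most of this stands.

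- **A reader might infer that power is stuck at .80.** Section 6.7 does not support that. There .80 is a chosen target, from which f2 = .037 was derived, under an assumption the plan itself calls extremely conservative. The planned covariates may already lift it. The 216 reflects loss at follow-up assessment ("216 participants are assessed at 12-month follow-up"), whereas these outcomes come from records and section 6.2 analyses everyone randomised.
- **A reader might infer that the models hold no baseline criminal-history information.** They hold age of onset of criminal activity, so only the increment beyond it counts.
- **Predictive strength may be modest.** Crime severity records the most serious lifetime level, not frequency. Everyone enrolled is a prisoner, so the range of histories may be restricted.
- **Events may be few.** At 10% of 216 there are about 22 re-incarcerations, while 6.4.1 already carries seven terms (treatment, three covariates, three interactions). Events, not participants, limit the model.
- **Section 6.10 handles part of it.** It does name crime severity, and describes its models as sensitivity or subgroup analyses. But the covariates there are only possible ones, the focus is on interactions, and crime and incarceration histories are absent.

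These points reduce the size of the gain and shape the remedy. They do not explain why the closest baseline counterparts of two Aim 1 outcomes stay out of the main models.

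**Conclusion.** The point holds as a modest, nearly free improvement. The main models for re-arrest and re-incarceration omit pre-randomisation measures that the trial already collects, and the plan does not say why.

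The size rests on an assumed increment in R2. At f2 = .037 and N = 216, power rises from about .80 to .82, .84 or .90 for a further 5%, 10% or 25% of the remaining variance. At event rates of about 20% or less, the likely gain is about 0 to 3 points unless the predictor is very strong. It would be tempting to read .84 to .90 as the power these outcomes are losing. That range needs an added R2 of .10 to .25, for which the documents give no support, and it starts from a figure that is conservative by design.

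**What to change.** In 6.4.1, for re-arrest and re-incarceration only, pre-specify two further main effects without treatment interactions:

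1. the 7-point baseline crime severity score;
2. one matching history measure from the baseline assessment, on a single stated scale: pre-incarceration crime (for example, days of crime) for re-arrest, and prior incarcerations for re-incarceration. Baseline arrest counts are not named in the documents, so the plan should not rely on them.

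State a rule, fixed before outcome data are seen, that keeps only the matching history measure if re-incarceration events are few. The rule should depend on the event count pooled over both arms. Use the same covariates whether the model is logistic or time-to-event, since Figure 2 and section 6.5 leave that open. Keep the 6.10 models as exploratory.

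The cost is wording, with no new data or visits. Each model gives up one or two degrees of freedom, and the treatment effect must be reported as covariate-adjusted (conditional), which in a logistic or survival model differs from the unadjusted effect.
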